2.2.2.2. Secondary Efficacy Endpoints

The secondary efficacy endpoints of this study include the following:

- Body-IGA (B-IGA) Success at Week 8, defined as achievement of B-IGA score of “Clear” or “Almost Clear” plus a 2-grade improvement from baseline
- Psoriasis Scalp Severity Index (PSSI)-75 (subjects who achieve a 75% reduction in PSSI from Baseline) at Week 8
- For subjects with baseline Scalp Itch - Numeric Rating Scale (SI-NRS) score ≥ 4 , achievement of ≥ 4 -point improvement from baseline in SI-NRS at Week 8
- For subjects with baseline SI-NRS score ≥ 4 , achievement of ≥ 4 -point improvement from baseline in SI-NRS at Week 4
- For subjects with baseline SI-NRS score ≥ 4 , achievement of ≥ 4 -point improvement from baseline in SI-NRS at Week 2
- Time to success in PSSI-50
- Change and percent change from baseline in total Psoriasis Symptoms Diary (PSD) score at Week 8
- Change and percent change from baseline in total PSD score at Week 4
- PSSI-90 (subjects who achieve a 90% reduction in PSSI from Baseline) at Week 8

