- **CDLQI Score** = sum of the 10 questions (individual questions scored as Very much=3, Quite a lot=2, Only a little=1, Not at all=0; Question 7: if the last week was school time, the question was scored as Very much=3, Quite a lot=2, Only a little=1, Not at all=0, with Prevented school recoded to 3, and if the last week was vacation, the standard responses apply; range for score 0 to 30). If 1 item is missing, that item is scored as 0. If 2 or more items are missing, the score should not be calculated.

- **PSD Total score** = sum of the 16 questions (individual questions scored 0 to 10, where higher scores indicate more severe symptoms; range for total score 0 to 160). If 1 or more items are missing, the score is not calculated.
- **Compliance** = number of applications divided by the expected number of IP applications for each subject. Compliance will be calculated using drug accountability data over the entire treatment period for each subject, up to treatment completion or discontinuation.
 - **Number of expected IP applications** = 56 for subjects who complete the study or number of days between first and last application of IP (last treatment date - first treatment date + 1) for subjects who discontinue early from the study.
 - **Number of IP applications** = number of expected IP applications – missed IP applications as collected in the electronic case report form (eCRF).
- **Weight of IP (g)** = returned can weight – dispensed can weight.
- **Body mass index (BMI) (kg/m²)** = [weight (kg) / height (cm) / height (cm)] x 10,000.
- **BMI Categories**
 - Underweight: BMI < 18.5
 - Normal: 18.5 ≤ BMI ≤ 24.9
 - Overweight: 25.0 ≤ BMI ≤ 29.9
 - Obese: BMI ≥ 30.0
- **Change from baseline** = value at current time point – value at baseline.
- **Treatment emergent AE (TEAE)** = any AE with an onset date/time after the first application of IP.
- **PHQ-8** = sum of the 8 questions (individual questions scored as Not at all=0, Several days=1, More than half the days=2, and Nearly every day=3; range for score 0 to 24). If more than 1 item is missing, the score should not be calculated. If 1 item is missing, the score is calculated as (sum of answered items*8)/number of answered items.

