Summary and Change from Baseline in PSSI Scores by Study Visit
ITT Population

Study Visit Statistic	Roflumilast Foam 0.3%		Vehicle (N=XX)	
	Observed	Change (N=XX)	Observed	Change
Baseline				
n	XX		XX	
Mean (SD)	XX.X (X.XX)		XX.X (X.XX)	
Median	XX.X		XX.X	
Min, Max	XX, XX		XX, XX	
Q1, Q3	XX.X		XX.X	
Week 2				
n	XX	XX	XX	XX
Mean (SD)	XX.X (X.XX)	XX.X (X.XX)	XX.X (X.XX)	XX.X (X.XX)
Median	XX.X	XX.X	XX.Xs	XX.X
Min, Max	XX, XX	XX, XX	XX, XX	XX, XX
Q1, Q3	XX.X	XX.X	XX.X	XX.X

Repeat for Week 4, Week 8, Week 9.

Abbreviation: PSSI = Psoriasis Scalp Severity Index.

Note: Subjects are summarized by planned treatment. PSSI total score is calculated as (erythema score + induration + desquamation) × extent of scalp affected. The score ranges from 0 to 72. Erythema, induration, and desquamation are scored on a scale of 0 to 4, where 0 = absent and 4 = severest possible; extent of scalp affected is scored on a scale of 0 to 6, where 0 = 0% of involved area and 6 = 90-100% of involved area. Baseline is the last non-missing measurement taken before the first application of study drug. Change from baseline is calculated as result – baseline result. Percent change from baseline is calculated as (change from baseline/baseline) *100.

Reference Listing: 16.2.6.3

Table 14.2.3.2
Summary and Change from Baseline in PSSI Scores by Study Visit
mITT Population

(Programming note: Same as table 14.2.3.1)

Table 14.2.3.3
Summary of Achievement of PSSI-50, PSSI-75, PSSI-90, and PSSI-100 by Study Visit
ITT Population

Study Visit Category/Statistic	Roflumilast Foam 0.3% (N=XX)	Vehicle (N=XX)
Week 2	XX	XX
PSSI-50 [1]		
Yes	XX (XX.X%)	XX (XX.X%)
95% CI [5]	(X.XX, X.XX)	
No	XX (XX.X%)	XX (XX.X%)
Odds Ratio (95% CI) [6]	X.XX (X.XX, X.XX)	
P value [6]	X.XXXXX	
PSSI-75 [2]		
Yes	XX (XX.X%)	XX (XX.X%)
95% CI [5]	(X.XX, X.XX)	(X.XX, X.XX)
No	XX (XX.X%)	XX (XX.X%)
Odds Ratio (95% CI) [6]	X.XX (X.XX, X.XX)	X.XX (X.XX, X.XX)
P value [6]	X.XXXXX	

Continue for PSSI-90 [3] and PSSI-100 [4]; Repeat for Week 4, Week 8, and Week 9.

Abbreviations: B-IGA = body investigator global assessment; CI = confidence interval; S-IGA = scalp investigator global assessment; PSSI = Psoriasis Scalp Severity Index.

Note: Percentages are n/Number of subjects in the ITT population within planned treatment at each visit*100. Baseline is the last non-missing measurement taken before the first application of study drug.

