[1] Estimates for LS means (change/percent change from baseline and difference from vehicle [i.e., change/percent change from baseline for roflumilast foam 0.3% minus change from baseline for vehicle]) and accompanying 95% CIs, and P values are from an ANCOVA with country, baseline S-IGA score category, baseline B-IGA score category, and baseline PSSI score as independent variables. Baseline is the last non-missing measurement taken before the first application of study drug. Percent change from baseline is calculated as (result – baseline result)*100.

[2] P value for testing change/percent change from baseline is zero.

[3] P value for testing difference (roflumilast foam 0.3% minus vehicle) in change/percent change from baseline from is zero.

Reference Listings: 16.2.6.1, 16.2.6.2, 16.2.6.5

Table 14.2.3.8
Summary of PSSI Scores by Study Visit – ANCOVA
mITT Population

(Programming note: Same as table 14.2.3.7.)

Table 14.2.4.1
Summary and Change from Baseline in Scalp Itch – Numeric Rating Scale (SI-NRS) Pruritus Score by Study Visit
ITT Population

(Programming note: Same as table 14.2.3.1. Update abbreviation row to display “SI-NRS = Scalp Itch – Numeric Rating Scale”. Change reference listing to Reference Listing: 16.2.6.4. Update the footnotes as “Note: Subjects are summarized by planned treatment. The SI-NRS will be determined by asking the subject’s assessment of worst itch of scalp over the past 24 hours. The scale is from 0 to 10, which ranges from “no scalp itch” to “worst scalp itch imaginable”. Baseline is the last non-missing measurement taken on or before the day of first application of study drug. Change from baseline is calculated as result – baseline result. Percent change from baseline is calculated as (change from baseline/baseline)*100.”)

Table 14.2.4.2
Summary and Change from Baseline in Scalp Itch – Numeric Rating Scale (SI-NRS) Pruritus Score by Study Visit
mITT Population

(Programming note: Same as table 14.2.4.1.)

Table 14.2.4.3
Scalp Itch – Numeric Rating Scale (SI-NRS) Pruritus Score Success by Study Visit
ITT Population, Subjects with SI-NRS Pruritus Score ≥ 4 at Baseline (SPRU4-ITT Population)

Study Visit/ Category/Statistic	Roflumilast Foam 0.3% (N=XX)	Vehicle (N=XX)
Week 2	XX	XX
SI-NRS Success [1]		
Yes	XX (XX.X%) (X.XX, X.XX)	XX (XX.X%) (X.XX, X.XX)
95% CI [2]	XX (XX.X%)	XX (XX.X%)
No		
Odds Ratio (95% CI) [3]	X.XX (X.XX, X.XX)	
P value [3]	X.XXXXX	

Repeat for all Week 4, Week 8, and Week 9.

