(Programming note: Same as table 14.2.3.7. Update [1] as to use “PSD total score” instead of “PSSI score”. Change abbreviation from PSSI to PSD = Psoriasis Symptom Diary. Change reference listings to Reference Listings: 16.2.6.1, 16.2.6.2, 16.2.6.5. Update the Note as “Note: Subjects are summarized by planned treatment. Baseline is the last non-missing measurement taken before the first application of study drug. PSD total score is calculated as sum of the 16 questions (individual questions scored 0 to 10, where higher scores indicate more severe symptoms). The score ranges from 0 to 160. If 1 or more items are missing, the score is not calculated.”)

Table 14.2.5.4
Summary of Psoriasis Symptom Diary (PSD) Total Scores by Study Visit – ANCOVA
mITT Population

(Programming note: Same as table 14.2.5.3.)

Table 14.2.6.1
Summary and Change from Baseline in PASI/mPASI by Study Visit
ITT Population

(Programming note: Same as table 14.2.3.1, except add header rows at the top for “Scale: PASI” or “Scale: mPASI”. Add Abbreviations “PASI = Psoriasis Area Severity Index” and “mPASI = modified PASI” in alphabetical order. Change reference listing to Reference Listings: 16.2.6.1, 16.2.6.2, 16.2.6.6. Update [1] as “PASI is calculated as $(0.1 \times [Eh + Th + Sh] \times Ah) + (0.2 \times [Ea + Ta + Sa] \times Aa) + (0.3 \times [Et + Tt + St] \times At) + (0.4 \times [Ei + Ti + Si] \times Ai)$, where E, T, and S are erythema, thickness, and scaling, respectively, scored on a scale of 0 to 4, A is estimated area of skin involved, graded on a scale of 0 to 6, and h, e, t, and l are head, arms, trunk, and legs respectively. The total score ranges from 0 to 72. mPASI is calculated similar to PASI except that for subjects with < 10% of any particular involved anatomic area, the mPASI will be calculated using the actual percentage of the anatomical area involved rather than the 0 to 6 estimated area score (e.g., 0.1 for 1%, 0.2 for 2%, 0.3 for 3%, ... 0.9 for 9%). Lower scores indicate improvement. Change from baseline is calculated as result – baseline result. Percent change from baseline is calculated as $(\text{change from baseline}/\text{baseline}) \times 100$.”)

Table 14.2.6.2
Summary and Change from Baseline in PASI/mPASI by Study Visit
mITT Population

(Programming note: Same as table 14.2.6.1)

Table 14.2.6.3
Summary of PASI/mPASI by Study Visit – ANCOVA
ITT Population

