(Programming note: Same as table 14.2.3.1. Change reference listing to Reference Listing: 16.2.6.7. Update abbreviation row to display “WI-NRS = Worst Itch – Numeric Rating Scale”. Update footnote as follows: “Note: Subjects are summarized by planned treatment. The WI-NRS will be determined by asking the subject’s assessment of worst itch over the past 24 hours. The scale is from 0 to 10, which ranges from “no itch” to “worst imaginable itch”. Baseline is the last non-missing measurement taken on or before the day of first application of study drug. Change from baseline is calculated as result – baseline result. Percent change from baseline is calculated as (change from baseline/baseline)*100.”)

Table 14.2.7.2
Summary and Change from Baseline in Worst Itch – Numeric Rating Scale (WI-NRS) by Study Visit
mITT Population

(Programming note: Same as table 14.2.7.1)

Table 14.2.7.3
Summary of Worst Itch – Numeric Rating Scale (WI-NRS) by Study Visit – ANCOVA
ITT Population

(Programming note: Same as table 14.2.3.7; Replace instances of PSD with WI-NRS in [1]. Change reference listings to Reference Listings: 16.2.6.1, 16.2.6.2, 16.2.6.7. Update abbreviation row to display “WI-NRS = Worst Itch – Numeric Rating Scale”. Update the baseline definition to read, “Baseline is the last non-missing measurement taken on or before the day first application of study drug.” Replace PSD Total Score text in the note footnote with “The WI-NRS will be determined by asking the subject’s assessment of worst itch over the past 24 hours. The scale is from 0 to 10, which ranges from “no itch” to “worst imaginable itch”. Lower scores indicate improvement.”)

Table 14.2.7.4
Summary of Worst Itch – Numeric Rating Scale (WI-NRS) by Study Visit – ANCOVA
mITT Population

(Programming note: Same as table 14.2.7.3)

Table 14.2.7.5

Worst Itch – Numeric Rating Scale (WI-NRS) Pruritus Score Success by Study Visit
ITT Population, Subjects with WI-NRS Pruritus Score ≥ 4 at Baseline (PRU4-ITT Population)

(Programming note: Same as table 14.2.4.3, except replace all instances of SI-NRS with WI-NRS. Update abbreviation row to display “WI-NRS = Worst Itch – Numeric Rating Scale”. Change reference listings to Reference Listings: 16.2.6.1, 16.2.6.2, 16.2.6.7.)

Table 14.2.7.6

Worst Itch – Numeric Rating Scale (WI-NRS) Pruritus Score Success by Study Visit
mITT Population, Subjects with WI-NRS Pruritus Score ≥ 4 at Baseline (PRU4-mITT Population)

(Programming note: Same as table 14.2.7.5.)

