(Programming note: Same as table 14.2.3.7. Add “BSA = body surface area” and “ePRO = electronic patient reported outcomes” to abbreviations in alphabetical order. Change reference listings to Reference Listings: 16.2.6.1, 16.2.6.2, 16.2.6.9. Replace instances of PSD with BSA in [1]. Replace PSD Total Score text in the note footnote with “BSA collected on the ePRO tablet will be used for summarization.”)

Table 14.2.9.4
Summary of % Body Surface Area (BSA) Affected by Disease by Study Visit – ANCOVA
mITT Population

(Programming note: Same as table 14.2.9.3)

Table 14.3.1.1
Summary of Treatment Emergent Adverse Events
Safety Population

Category	Roflumilast Foam 0.3% (N=XX)	Vehicle (N=XX)	Overall (N=XX)
Subjects with at least 1 TEAE	XX (XX.X%)	XX (XX.X%)	XX (XX.X%)
Maximum Severity of TEAE [1]			
Grade 1 (Mild)	XX (XX.X%)	XX (XX.X%)	XX (XX.X%)
Grade 2 (Moderate)	XX (XX.X%)	XX (XX.X%)	XX (XX.X%)
Grade 3 (Severe)	XX (XX.X%)	XX (XX.X%)	XX (XX.X%)
Grade 4 (Life-threatening consequences)	XX (XX.X%)	XX (XX.X%)	XX (XX.X%)
Grade 5 (Death related to AE)	XX (XX.X%)	XX (XX.X%)	XX (XX.X%)
Subjects with a Related TEAE [2]	XX (XX.X%)	XX (XX.X%)	XX (XX.X%)
Subjects with a TEAE Leading to Discontinuation of Study Drug	XX (XX.X%)	XX (XX.X%)	XX (XX.X%)
Subjects with an SAE	XX (XX.X%)	XX (XX.X%)	XX (XX.X%)
Subjects with a Grade 5 TEAE [3]	XX (XX.X%)	XX (XX.X%)	XX (XX.X%)

Abbreviations: AE = adverse event; CTCAE = Common Terminology Criteria for Adverse Events; IP = investigational product; SAE = serious adverse event; TEAE = treatment emergent adverse event.

Note: Percentages are n/Number of subjects in the Safety population within treatment received*100. A TEAE is defined as an AE that started post application of IP at the baseline visit through study completion.

[1] Severity grades are reported according to the CTCAE version 4.0. Subjects are counted only once at the worst severity. If a severity designation is missing, it will be considered as severe.

[2] AEs with a relationship of possibly, probably, likely, or missing were considered related.

[3] A Grade 5 TEAE is a TEAE leading to death.

Reference Listing: 16.2.7.1

Table 14.3.1.2
Incidence of Treatment Emergent Adverse Events by System Organ Class and Preferred Term
Safety Population

System Organ Class Preferred Term	Roflumilast Foam 0.3% (N=XX)	Vehicle (N=XX)	Overall (N=XX)
Subjects with at least 1 TEAE	XX (XX.X%)	XX (XX.X%)	XX (XX.X%)
System Organ Class 1 Preferred Term 1	XX (XX.X%)	XX (XX.X%)	XX (XX.X%)

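### The SAP's ANCOVA table shells define percent change without dividing by baseline, contradicting the descriptive shells for the same variables; no controlled test is affected.

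*SAP*

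**What the plan says.** SAP 8.2.2, 8.2.3, 8.2.4 and 8.3 plan ANCOVAs of both change and percent change for PSSI, SI-NRS, PSD total score and the exploratory scores. SAP 2.2.2.2 also names percent change for the PSD among the secondary endpoints: "Change and percent change from baseline in total Psoriasis Symptoms Diary (PSD) score at Week 8".

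The formula for percent change appears only in the table shells of SAP 14.2, in two forms:

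- **ANCOVA shells.** Footnote [1] of Table 14.2.3.7 (PSSI) reads "Percent change from baseline is calculated as (result – baseline result)*100". The Note of Table 14.2.4.5 (SI-NRS) writes the same formula out again.
- **Descriptive shells.** Table 14.2.3.1 (PSSI) reads "Percent change from baseline is calculated as (change from baseline/baseline) *100". The descriptive shells for SI-NRS, PSD, PASI/mPASI, WI-NRS, DLQI/CDLQI and BSA (Tables 14.2.4.1, 14.2.5.1, 14.2.6.1, 14.2.7.1, 14.2.8.1 and 14.2.9.1) also divide by baseline.

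SAP 6.1.7, which lists the derived variables, defines change from baseline as "value at current time point – value at baseline" and gives no definition of percent change.

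**The concern.** A percent change needs the baseline as its denominator, and the ANCOVA formula has none. The omission occurs twice in full, and it spreads because the other ANCOVA shells are specified by reference to the PSSI one. With no governing definition in 6.1.7, a programmer has two conflicting instructions for a variable of the same name.

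At stake are the reported LS means, confidence intervals and p values for percent change, and whether the ANCOVA tables agree with the descriptive tables beside them. Even if the programmer ignores the footnote and does the right thing, the footnote is printed with the output, and the report then misdescribes how its numbers were derived.

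**Working it through.** **1. Which shells carry the formula.** I followed the cross-references in SAP 14.2.

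| ANCOVA shell (ITT) | How it is specified | Formula it carries |
|---|---|---|
| PSSI, 14.2.3.7 | written out in footnote [1] | no denominator |
| SI-NRS, 14.2.4.5 | based on 14.2.3.7; formula repeated in its Note | no denominator, twice |
| PSD, 14.2.5.3 | based on 14.2.3.7; "Update [1] as to use “PSD total score” instead of “PSSI score" | no denominator |
| PASI/mPASI, 14.2.6.3 | based on 14.2.5.3 | no denominator |
| WI-NRS, 14.2.7.3 | "Same as table 14.2.3.7; Replace instances of PSD with WI-NRS in [1" | no denominator |
| BSA, 14.2.9.3 | based on 14.2.3.7; "Replace instances of PSD with BSA in [1" | no denominator |
| DLQI/CDLQI, 14.2.8.3 | based on 14.2.3.7; its Note adds "Percent change from baseline is calculated as (change from baseline/baseline)*100" | both |

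The edits to footnote [1] change the name of the score and leave the formula alone. The mITT shells repeat their ITT counterparts.

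**2. What the formula returns.** Let b be baseline and r the later result.

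- ANCOVA footnote: F = (r - b) × 100
- Descriptive shells: P = (r - b)/b × 100

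So F = b × P. The two agree only if b = 1 or r = b; otherwise F differs from P by a factor equal to the baseline score. The values below are chosen for illustration and are not trial data.

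| Score | b | r | F | P (%) |
|---|---|---|---|---|
| PSSI | 20 | 8 | (8 - 20) × 100 = -1200 | -12/20 × 100 = -60 |
| PSSI | 24 | 6 | -1800 | -75 |
| PSSI | 6 | 3 | -300 | -50 |
| SI-NRS | 8 | 4 | -400 | -50 |
| PSD | 100 | 40 | -6000 | -60 |
| BSA | 10 | 5 | -500 | -50 |

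Protocol 4.4.1 requires a baseline PSSI of at least 6, so for any eligible subject whose PSSI changes, F is at least six times P. Complete clearance gives F = -600 from a baseline of 6 and F = -7200 from a baseline of 72; P is -100% in both cases.

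**3. What the ANCOVA would then show.** F is a constant multiple of absolute change. In a linear model with the same covariates, estimates and standard errors are multiplied by 100, and t and p are unchanged. I confirmed this on one simulated data set (200 active, 100 vehicle; model with treatment and baseline; all values invented):

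| Outcome | Treatment estimate | SE | t |
|---|---|---|---|
| Absolute change | -8.62 | 0.958 | -9.00 |
| F (footnote) | -861.9 | 95.8 | -9.00 |
| P (true percent change) | -30.3 | 3.16 | -9.57 |

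The footnote version adds nothing to the absolute-change analysis. True percent change is a different outcome with its own test statistic.

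**4. What the testing strategy uses.** SAP 6.1.3 and 8.2.4 admit only absolute change in PSD total score at Weeks 4 and 8. S-IGA and B-IGA success, the SI-NRS responder endpoints, PSSI-75, PSSI-90 and time to PSSI-50 have their own definitions in 6.1.7. None takes its value from the ANCOVA footnote.

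**5. Zero baselines.** P is undefined at b = 0. The SI-NRS and WI-NRS ANCOVAs use the full ITT and mITT populations, not the subsets with a baseline of at least 4, and the baseline table shell has a row for a score of 0 on both scales. PSD and DLQI/CDLQI totals can also be 0 under 6.1.7. The plan gives no rule for such subjects. The problem does not arise for PSSI (entry minimum 6) or PASI (entry minimum 2).

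**The case against.** The best defence is that this is a dropped denominator in a shell footnote and not a second definition. Each affected variable has a descriptive shell with the correct formula under the same name, and the analysis text in SAP 8.2.2 to 8.3 contains no faulty formula. The shells have other drafting slips; for example, the notes for the WI-NRS, DLQI/CDLQI and BSA ANCOVA tables ask for PSD to be replaced in a shell written for PSSI. A literal implementation would also be conspicuous: a score that cannot go below zero cannot fall by more than 100%, so a mean of several hundred would be noticed.

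Most of this stands, and it makes a correctly programmed analysis the likely outcome. It does not remove the defect, because the incorrect derivation would still be printed under the ANCOVA tables and would still contradict the tables next to them.

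A reader might infer three stronger things that the documents do not support:

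- **That every percent-change ANCOVA has only the wrong formula.** The DLQI/CDLQI shell also states the correct one; it contradicts itself.
- **That wrong values are certain.** They arise only if the footnote is programmed as written.
- **That a controlled secondary endpoint is at risk.** Percent change in PSD is listed in SAP 2.2.2.2, but only absolute change enters the testing strategy, and Protocol 6.3.2 lists only change from baseline for the PSD.

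**Conclusion.** The point holds as an internal contradiction in the SAP, with a formula that is wrong as written. It is stated in full in two ANCOVA shells, inherited by four more (PSD, PASI/mPASI, WI-NRS, BSA) and their mITT versions, and present alongside the correct formula in the DLQI/CDLQI shell. SAP 6.1.7 does not resolve it.

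If the footnote is followed literally, each value differs from the true percent change by a factor equal to the subject's baseline score, and the analysis reproduces the absolute-change p value. If it is not followed, the harm is confined to a misstated derivation in the report. I cannot tell from the documents which was programmed. In neither case does the primary result or any alpha-controlled secondary test change. The defect concerns reporting; it merits correction because the remedy is specific and nearly free.

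**What to change.** 1. Add to SAP 6.1.7: percent change from baseline = 100 × (result - baseline)/baseline, not calculated when baseline is 0.
2. Correct footnote [1] of Table 14.2.3.7 and the Note of Table 14.2.4.5 to this formula, and check that the correction carries through to the PSD, PASI/mPASI, WI-NRS, DLQI/CDLQI and BSA ANCOVA shells and all mITT versions. In Table 14.2.8.3 this removes the conflict between the Note and the inherited footnote.
3. Show the number of subjects analysed for percent change separately from the number analysed for change, since the zero-baseline rule can make them differ for SI-NRS, WI-NRS, PSD and DLQI/CDLQI.
4. If tables have already been programmed, check one subject's derived percent change against the formula.

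The cost is SAP wording and footnotes. Design, data collection, sample size and the testing strategy are untouched.
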